13.4 Participant and Data Confidentiality

Information about study subjects will be kept confidential and managed according to the requirements of the Health Insurance Portability and Accountability Act of 1996 (HIPAA). Those regulations require a signed subject authorization informing the subject of the following:

- What protected health information (PHI) will be collected from subjects in this study
- Who will have access to that information and why
- Who will use or disclose that information
- The rights of a research subject to revoke their authorization for use of their PHI.

In the event that a subject revokes authorization to collect or use PHI, the investigator, by regulation, retains the ability to use all information collected prior to the revocation of subject authorization. For subjects that have revoked authorization to collect or use PHI, attempts should be made to obtain permission to collect at least vital status (i.e. that the subject is alive) at the end of their scheduled study period.

Participant confidentiality is strictly held in trust by the participating investigators, their staff, and the sponsor(s) and their agents. This confidentiality is extended to cover testing of biological samples and genetic tests in addition to the clinical information relating to participants. Therefore, documentation, data, and all other information generated will be held in strict confidence. No information concerning the study or the data will be released to any unauthorized third party without prior written approval of the sponsor or

CONFIDENTIAL

the PI.

The study monitor, other authorized representatives of the sponsor, or representatives of the IRB may inspect all documents and records required to be maintained by the investigator, including but not limited to, medical records (office, clinic, or hospital) and pharmacy records for the participants in this study. The clinical study site will permit access to such records.

The study participant's contact information will be securely stored in the PI's office in the NYU Meyers College of Nursing for internal use during the study. Only the PI and study staff authorized by the PI will be allowed access to the document linking ID numbers to study participant's personally identifiable information. At the end of the study, all records will continue to be kept in a secure location for as long a period as dictated by IRB and institutional regulations.

Study participant research data, which is for purposes of statistical analysis and scientific reporting, will be transmitted to and stored in the research offices of the PI at the NYU Meyers College of Nursing. These data will be shared with study investigators and may be shared with non-study investigators for secondary analyses at the discretion of the PI. This will not include the participant's contact or identifying information. Rather, individual participants and their research data will be identified by a unique study identification number. The study data entry and study management systems used by clinical sites and by NYU Meyers College of Nursing research staff will be secured and password protected. At the end of the study, all study databases will be de-identified and archived at the NYU Meyers College of Nursing. Blood samples will be identified only by a study ID number and stored in the B3 biobank in the College of Dentistry until genomic data collection. Data generated in genomic data collection will be transferred to the research offices of the PI and shared as described herein. MRI scans will be stored on secure servers at the Center for Brain Imaging. Scans will be transferred when ready for pre-processing and analysis to the research offices of the PI and shared as described herein.

To further protect the privacy of study participants, a Certificate of Confidentiality will be obtained from the NIH. This certificate protects identifiable research information from forced disclosure. It allows the investigator and others who have access to research records to refuse to disclose identifying information on research participation in any civil, criminal, administrative, legislative, or other proceeding, whether at the federal, state, or local level. By protecting researchers and institutions from being compelled to disclose information that would identify research participants, Certificates of Confidentiality help achieve the research objectives and promote participation in studies by helping assure confidentiality and privacy to participants.

Genomic Data Sharing Plan. The R00 study will not produce large-scale human genomic data (i.e., at least 100 samples for RNA-seq). Therefore, the NIH Genomic Data Sharing Policy does not require submission of the data to an NIH-designated repository. Currently, the maximum number of samples that will be submitted for RNA-seq using samples collected during the R00 study will be 96. However, it is unlikely that the investigators will successfully collect RNA-seq data from all samples.

If the maximum number of samples from which RNA-seq data is successfully collected were to exceed the threshold for data sharing (due to, for example, securing additional funds to increase sample size), the appropriate program official at the NINR will be notified, and a detailed plan for sharing of generated data will be developed. In that case, it is anticipated that the study will be registered in dbGaP and that gene expression data and associated phenotypic data will be submitted to an NIH-designated data repository (e.g., Gene Expression Omnibus [GEO]) so that it can be released no later than six months after initial data submission begins, or at the time of acceptance of the first publication, whichever occurs first. To allow for this possibility, the consent form for the R00 study will be worded to allow broad data sharing, should it become necessary.

Even though the R00 study is not anticipated to reach the threshold for required genomic data sharing, the study will have in place plans for sharing de-identified data for secondary analyses with qualified investigators. The consent language for the R00 study will be worded for possible broad data sharing, as described above. The investigators also plan to submit genomic data and relevant phenotypic data (e.g., clinical characteristics of the sample) generated in the R00 study to an NIH-designated data

CONFIDENTIAL

repository in a timely manner. In this case, the timeline for submission to an NIH-designated data repository will allow first for publication of findings related to the aims of the R00 study, as well as submission as preliminary data for anticipated R01 grant application(s). The submission process will likely include registration in dbGaP and submission to GEO for controlled access to the data.

13.5 Research Use of Stored Human Samples, Specimens, and Data

- **Intended Use:** Samples and genomic data collected under this protocol may be used to study relationships between genes or gene products and neural markers of changes in cognitive function, for exploratory analyses consistent with the SAP, and for any purpose described in the Genomic Data Sharing Plan. To accomplish these aims, study samples may be shipped to locations outside NYU for processing and data collection. Any samples so shipped will be returned to the B3 after data collection for future storage. Any data generated in said process will be returned to the PI at the NYU Meyers College of Nursing and shared as described herein.
- **Storage:** Access to stored samples in the B3 will be limited to study investigators and their approved staff. Samples and genomic data will be stored using codes assigned by the investigators. Genomic data generated from the samples will be kept in University-approved encrypted, password-protected servers. Only investigators and their approved staff will have access to the samples and data.
- **Tracking:** Sample location and linking information are managed by a commercial specimen tracking system. [name], a study team member, is Director of B3.
 - **Disposition at the completion of the study:** All stored samples remain in B3 until used completely. Study participants who request destruction of samples will be notified of compliance with such request and all supporting details will be maintained for tracking.

13.6 Future Use of Stored Human Samples, Specimens, and Data

Participants may provide optional permission for future broad use of their stored samples, specimens, and data after the study is completed. We do not yet know the purpose of such future research, which could be related to any of the samples, specimens, or data collected as part of the study.

After the study is completed, the de-identified, archived data will remain at NYU, under the supervision of the PI, for use by other researchers including those outside the study. These other researchers may include the PI's students, other researchers at NYU, or researchers at other institutions. The PI will monitor the research activities of students and other researchers at NYU to ensure that data generated in this study are used appropriately. Data shared with researchers at other institutions via NIH databases will be covered under the NINR-approved Genomic Data Sharing Plan. The PI will enter into Data Use Agreements with researchers at other institutions not covered under this plan. The optional permission for future use includes future uses that are unknown at this time, so the PI will ensure that any such future uses are appropriate.

These biological samples will be stored indefinitely at the B3 until used up. The samples could be used for research consistent with this protocol, for research consistent with the genomic data sharing plan, or for broad use with any data collected as part of the study. True genetic testing is not planned for these samples or specimens. Samples, specimens, and data will be labeled using codes assigned by study investigators. Data will be stored in University-approved, encrypted, cloud-based storage (e.g., Box), which is password protected. With the exception of NIH databases, any data shared with secondary investigators will be accessed by them using shared Box folders. Study investigators and their approved staff will have access to the samples and data. Secondary investigators will be granted access to the data with time, as consistent with the Genomic Data Sharing Plan.

Sample location and linking information will be managed in B3 by a commercial specimen tracking system. The PI will maintain a code-link that will allow linking the biological specimens with the phenotypic data from each participant, maintaining the masking of the identity of the participant. This code link will be shared with approval by the PI. Some data collected as part of the study may constitute a Limited Data Set, which will be shared with researchers at other institutions only as approved by the University in Data Use Agreements.

CONFIDENTIAL

During the conduct of the study, an individual participant can choose to withdraw consent to have samples, specimens, and data stored for future research by contacting the PI in writing. However, withdrawal of consent for storage will not be possible after the study is completed.

14 Data Handling and Record Keeping

14.1 Data Collection and Management Responsibilities

Data collection is the responsibility of the clinical trial staff at the site under the supervision of the site PI. The investigator is responsible for ensuring the accuracy, completeness, legibility, and timeliness of the data reported.

All source documents should be completed in a neat, legible manner to ensure accurate interpretation of data. Black ink is required to ensure clarity of reproduced copies. When making changes or corrections, cross out the original entry with a single line, and initial and date the change. **DO NOT ERASE, OVERWRITE, OR USE CORRECTION FLUID OR TAPE ON THE ORIGINAL.**

Copies of the electronic CRF (eCRF) will be provided for use as source documents and maintained for recording data for each participant enrolled in the study. Data reported in the eCRF derived from source documents should be consistent with the source documents, or the discrepancies should be explained and captured in a progress note and maintained in the participant's official electronic study record. Data obtained from paper source documents (e.g., patient-reported outcomes) will be entered twice and compared to reduce potential for data entry error.

Data generated in the study and clinical data entered directly from source documents (e.g., AEs, concomitant medications) will be entered into the SPSS dataset maintained by the PI and approved study staff. The dataset will be password protected and will be examined for data that appear inconsistent, incomplete, or inaccurate.

14.2 Study Records Retention

Study documents will be retained for at least the longest of 3 years after closeout, 3 years after the date of Federal Financial Report (FFR) submission, or 5 years after final reporting/publication. These documents may be retained for a longer period, however, if required by local regulations or if data analysis remains ongoing (e.g., secondary analyses). No records will be destroyed without the written consent of the PI.

14.3 Protocol Deviations

A protocol deviation is any noncompliance with the clinical trial protocol, GCP, or MOP requirements. The noncompliance may be either on the part of the participant, an investigator, or the study staff. As a result of deviations, corrective actions are to be developed and implemented promptly.

These practices are consistent with ICH E6:

- 4.5 Compliance with Protocol, sections 4.5.1, 4.5.2, and 4.5.3
- 5.1 Quality Assurance and Quality Control, section 5.1.1
- 5.20 Noncompliance, sections 5.20.1, and 5.20.2.

It is the responsibility of the site to use continuous vigilance to identify and report deviations within 3 working days of identification of the protocol deviation, or within 3 working days of the scheduled protocol-

required activity. All deviations must be addressed in study source documents, reported to the NINR Program Official and the data and safety monitoring team. Protocol deviations must be reported to the local IRB per their guidelines. The site PI and study staff are responsible for knowing and adhering to their IRB requirements. Further details about the handling of protocol deviations will be included in the MOP.

CONFIDENTIAL

14.4 Publication and Data Sharing Policy

Data will be shared with study investigators, with secondary investigators as approved by the PI, and as described in the genomic data sharing plan for the purpose of disseminating findings to the scientific community and to the public. This study will comply with the NIH Public Access Policy, which ensures that the public has access to the published results of NIH funded research. It requires scientists to submit final peer-reviewed journal manuscripts that arise from NIH funds to the digital archive PubMed Central upon acceptance for publication.

The International Committee of Medical Journal Editors (ICMJE) member journals have adopted a clinical trials registration policy as a condition for publication. The ICMJE defines a clinical trial as any research project that prospectively assigns human subjects to intervention or concurrent comparison or control groups to study the cause-and-effect relationship between a medical intervention and a health outcome. Medical interventions include drugs, surgical procedures, devices, behavioral treatments, process-of-care changes, and the like. Health outcomes include any biomedical or health-related measures obtained in patients or participants, including pharmacokinetic measures and adverse events. The ICMJE policy, and the Section 801 of the Food and Drug Administration Amendments Act of 2007, requires that all clinical trials be registered in a public trials registry such as ClinicalTrials.gov, which is sponsored by the National Library of Medicine. Other biomedical journals are considering adopting similar policies. For interventional clinical trials performed under NIH IC grants and cooperative agreements, it is the grantee's responsibility to register the trial in an acceptable registry, so the research results may be considered for publication in ICMJE member journals. The ICMJE does not review specific studies to determine whether registration is necessary; instead, the committee recommends that researchers who have questions about the need to register err on the side of registration or consult the editorial office of the journal in which they wish to publish.

FDAAA mandates that a "responsible party" (i.e., the sponsor or designated principal investigator) register and report results of certain "applicable clinical trials." NIH grantees, such as the R00 study PI, will take specific steps to ensure compliance with NIH implementation of FDAAA, including registering the trial with clinicaltrials.gov.

15 Study Finances

15.1 Funding Source

This study is funded through a grant from the National Institute of Nursing Research (R00NR015473).

15.2 Costs to the Participant

Participants will not be charged for any procedures of this study.

15.3 Participant Reimbursements or Payments

Participants will receive a modest compensation of \$100 for the two-part pre-intervention assessment, which includes MRI and neuropsychological testing; \$75 for the post-intervention assessment, which does not include neuropsychological testing; and \$75 for the three-month follow-up visit, which does not include MRI (total compensation of \$250 if all three study visits are completed). Participants will receive reimbursement for public transit or parking at NYU for each of the study assessment visits. Parking fines will not be reimbursed. Reimbursements for public transit or parking at NYU may be provided for the MBSR or HEP visits.

16 Study Administration

16.1 Study Leadership

The study team will govern the conduct of the study. The study team will be composed of the PI, study investigators, and representatives of NINR, as listed in section 1. With the exception of NINR personnel, who will meet with the study team when required, the PI will schedule monthly study team meetings. In addition, the PI will meet individually with study team members as needed.

CONFIDENTIAL

17 Conflict of Interest Policy

The independence of this study from any actual or perceived influence is critical. Therefore, any actual conflict of interest of persons who have a role in the design, conduct, analysis, publication, or any aspect of this trial will be disclosed and managed. Furthermore, persons who have a perceived conflict of interest will be required to have such conflicts managed in a way that is appropriate to their participation in the trial. The study leadership in conjunction with the NINR has established policies and procedures for all study group members to disclose all conflicts of interest and will establish a mechanism for the management of all reported dualities of interest.

Any investigator who has a conflict of interest with this study (patent ownership, royalties, or financial gain greater than the minimum allowable by their institution, etc.) must have the conflict reviewed by the NYU Langone Conflict of Interest Committee with a Committee-sanctioned conflict management plan that has been reviewed and approved by the study sponsor prior to participation in this study. All NYU Langone Health investigators will follow the applicable conflict of interest policies.

CONFIDENTIAL

18 References

Activity	Recruitment ≤ 3 months before enrollment	Enrollment TP0 - Day 1	Enrollment TP0 - Day 2	Intervention ≤ 3 weeks after	Week 2	Week 3	Week 4	Week 5	Week 6	Week 7	Week 8	Follow-up TP1 ≤ 3 weeks after	Final study visit (TP2) 3 months after +/- 1.5 weeks
Study team procedures													
Screen for eligibility	X												
Preliminary MRI safety screen	X												
Schedule enrollment	X												
Verify eligibility has not changed		X										X	X
Study consent		X											
Blood samples		X										X	X
Demographic and clinical data		X											
Update demos and clinicals												X	X
Assess for AEs, SAEs, UPs												X	X
Patient-reported outcomes (PROs)		X										X	X
Neuropsychological testing		X											X
Verbal IQ (NART-R)		X											
Confirm MRI safety			X									X	
Toxicology screen			X									X	
Practice MRI task			X									X	
Behavioral Handedness Index			X										
Confirm completion of PROs			X										
MRI scan			X									X	
Study assessment questionnaire			X									X	X

CONFIDENTIAL

This material is the property of the NYU College of Nursing and NYU Langone Health. Do not disclose or use except as authorized in writing by the study sponsor.
Behavioral Intervention Template Version: 5 MAY 2017.

Weekly REDCap diary				X	X	X	X	X	X	X	X	X	X
Remind about aggregate findings													X
AE instruction													X
Interventionist procedures													
Weekly MBSR or HEP meeting				X	X	X	X	X	X	X	X		
Daily homework				X	X	X	X	X	X	X	X		
One-day retreat										X*			

*The one-day retreat may be scheduled in week 6 or 7 of the intervention.

CONFIDENTIAL

**Statistical Analysis Plan (SAP) for R00NR015473**  
**August 8, 2017**

**Data analysis.** Data analysis will be performed using SPSS Statistics 24 (IBM Corp., Armonk, NY). Using exploratory and descriptive analyses, we will first evaluate whether any data anomalies (e.g., nonrandom missing data, erroneous outliers, multicollinearity, possible confounding) may invalidate planned analyses and then summarize data in terms of location and variability using appropriate descriptive statistics, given the variable's level of measurement and observed data distribution. As needed, appropriate remedial approaches (e.g., data transformations, imputation, nonparametric analysis methods) will be applied.

**Aim 1: Evaluate the preliminary efficacy of MBSR to improve neural markers of cognitive changes during AI therapy.** **fMRI:** Data will be preprocessed using Statistical Parametric Mapping-12 (SPM-12; [www.fil.ion.ucl.ac.uk/spm](http://www.fil.ion.ucl.ac.uk/spm)) to normalize images into standard space so that all brains can be compared. Talairach PickAtlas will be used to define regions of interest (ROIs) for cognitive and emotion processing. Neural activation will be evaluated using the blood-oxygen-level-dependent (BOLD) signal. SPM-12 will extract BOLD activation in these ROIs. Brain activation maps will describe (1) between-group differences in brain activation in ROIs for the MBSR versus active control group pre- and post-intervention and (2) within-group change scores in brain activation for each group pre- to post-intervention. **fcMRI:** BOLD signal time series will be extracted from ROIs of the default mode network. Physiological noise and motion artifact regressors will be removed. Residual time series from each ROI will be filtered between 0.01-0.08 Hz. Analyses will be performed with and without a global signal regressor to assess impact on connectivity. Parameter estimates representing connectivity between neural regions will be extracted. Functional connectivity maps will describe between-group differences in connectivity in ROIs pre- and post-intervention and within-group change scores in connectivity pre- to post-intervention. **dMRI:** Data will be analyzed using ExploreDTI ([www.exploredti.com](http://www.exploredti.com)), FreeSurfer ([surfer.nmr.mgh.harvard.edu](http://surfer.nmr.mgh.harvard.edu)), and the diffusion toolbox of the Functional MRI tool of Brain Software Library ([www.fmrib.ox.ac.uk/fsl](http://www.fmrib.ox.ac.uk/fsl)) to perform quality assurance for images, process them for characterization of the integrity of white matter tracts, and match white matter tracts to structural MRI data. White matter tracts between cortical and subcortical ROIs will be evaluated to describe how white matter integrity is affected. Fractional anisotropy (FA) values for white matter tracts will be extracted. FA maps will describe (1) between-group differences in FA in ROIs for the MBSR versus active control group pre- and post-intervention and (2) within-group change scores in FA pre- to post-intervention.

**Exploratory Aim 2a: Describe relationships between neural markers and changes in cognitive function.** Change scores for neuroimaging parameters obtained in Aim 1 will be correlated with change scores on measures of cognitive function to describe how neural markers are associated with cognitive changes. If no changes in neural markers are found, relationships between baseline neural markers and changes in cognitive function will be described. **Exploratory Aim 2b: Describe relationships between neural markers and changes in affect.** The methods in 2a will be used to describe relationships between neural markers and changes in affect. **Exploratory Aim 3: Explore the moderating effect of inter-individual differences in the expression of genes involved in stress responses on the relationship between AI therapy and neural markers during MBSR.** Differential expression (DE) of genes in relation to fMRI, fcMRI, and dMRI parameter estimates at each time point will be determined using correlational analysis. Expression intensity varies widely over genes and needs to be adjusted between genes to provide a reliable measure of DE. We will adjust the standard errors and estimate the correlation of genes with each outcome. We will adjust for multiple hypothesis testing through estimation of the FDR using the Benjamini-Hochberg procedure. The FDR q-value will be determined empirically.

**Possible Problems and Solutions.** The sample size is too small to make inferences about relationships evaluated in the R00 study to the larger population of postmenopausal women with breast cancer. The effect sizes for these relationships will be determined in the R00 study, which will inform the sample size for a well-powered study planned for future R01 applications (see Plan for Research Independence in the Final Progress Report for the K99 Phase). If no relationships are found between gene expression levels for stress response pathways and neural markers, other pathways will be evaluated (e.g., DNA repair).

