4.2 Study Endpoints

4.2.1 Primary Study Endpoints

As this pilot randomized controlled trial is designed to provide preliminary efficacy for a future well-powered R01 application, the primary endpoint (i.e., preliminary efficacy) will be evaluated using effect sizes for neural markers of changes in cognitive function from before to after MBSR versus HEP.

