10.4.2 Analysis of the Primary Efficacy Endpoint(s)

See SAP.

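### SAP Aim 1 does not name the primary contrast (MBSR versus HEP difference in before-to-after change) or the SD that standardises it

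*SAP*

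**What the plan says.** Protocol section 4.2.1 sets the primary endpoint as "effect sizes for neural markers of changes in cognitive function from before to after MBSR versus HEP". Section 10.4.2, which should give the primary analysis, only points to the SAP.

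SAP Aim 1 then describes three imaging modalities:

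- Task fMRI: "between-group differences in brain activation in ROIs for the MBSR versus active control group pre- and post-intervention and (2) within-group change scores".
- Resting-state connectivity: "between-group differences in connectivity in ROIs pre- and post-intervention and within-group change scores in connectivity pre- to post-intervention".
- Diffusion MRI: "between-group differences in FA in ROIs for the MBSR versus active control group pre- and post-intervention and (2) within-group change scores in FA".

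Around this, the SAP's data analysis paragraph says the team will "summarize data in terms of location and variability using appropriate descriptive statistics". Exploratory Aim 2a states that "Change scores for neuroimaging parameters obtained in Aim 1 will be correlated with change scores on measures of cognitive function", so a change score will exist for each participant. The only mention of effect sizes in the SAP is under Possible Problems and Solutions, where they are undefined and are described as something "which will inform the sample size for a well-powered study planned for future R01 applications".

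Protocol section 10.5 plans on an effect size of 1 with 16 per group. It does not say whether the effect is in the post-intervention value or the change, or which SD scales it.

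**The concern.** The endpoint compares change between arms. Aim 1 lists group differences at each scan and change inside each arm. It has no between-arm difference in change, group-by-time term, baseline-adjusted difference, interval or standardiser.

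The listed summaries are not good stand-ins. The post-intervention difference alone ignores the TP0 scan and so keeps whatever part of a chance baseline imbalance persists to TP1. Change within one arm mixes the intervention with the passage of time and, under inclusion criterion 9 in section 5.1, with AI therapy that may begin between TP0 and TP1. For the EFNBACK task it also includes the effect of doing the task a second time.

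The study makes no inferential claim (section 10.2); what it delivers is effect sizes for planning a later trial. The contrast, its precision and its units are therefore the main product, and they should be fixed before results are seen.

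**Working it through.** **1. The plan's own figure.** Inputs from section 10.5: 16 per arm, effect size 1, two-sided alpha 0.05, equal-variance t-test. The noncentral t has df = 30 and noncentrality 1 × √(16/2) = 2.83. Power is 78.14%, against the stated 78.1%, so the figure reproduces.

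**2. Where the definition might be.**

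| Place | What it supplies | What it lacks |
|---|---|---|
| Protocol 4.2.1 | change, MBSR versus HEP | estimator, SD |
| Protocol 10.2 | a promise of effect sizes | definition |
| Protocol 10.5 | planning effect of 1, pooled-variance test | outcome variable, SD |
| SAP Aim 1 | group difference at each scan; change in each arm | difference in change, interval, SD |
| SAP Aim 2a | per-participant change scores | between-arm comparison |

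Subtracting one arm's mean change from the other's gives the raw contrast, and the arm-level SDs of change would give its standard error. The gap is one of specification; the data are sufficient.

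**3. Precision of the candidate estimators.** The documents give no TP0-TP1 correlation (rho). I assume 0.3, 0.5 and 0.7, equal SDs at both scans and independent participants. In units of the single-time-point SD:

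- Half-width = t(0.975, df) × √((2/16) × V), with √(2/16) = 0.354.
- Post-intervention only: V = 1, df 30, t = 2.042.
- Change score: V = 2(1 − rho), df 30.
- Adjusted for TP0 and chemotherapy stratum: V = 1 − rho², df 28, t = 2.048.

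| rho | Adjusted | Change score | Post only |
|---|---|---|---|
| 0.3 | 2.048 × 0.354 × √0.91 = 0.69 | 2.042 × 0.354 × √1.4 = 0.85 | 0.72 |
| 0.5 | 2.048 × 0.354 × √0.75 = 0.63 | 2.042 × 0.354 × √1.0 = 0.72 | 0.72 |
| 0.7 | 2.048 × 0.354 × √0.51 = 0.52 | 2.042 × 0.354 × √0.6 = 0.56 | 0.72 |

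The adjusted estimate is narrowest at each assumed rho. Its lead over the post-only difference is small at rho 0.3, and its lead over the change score is small at rho 0.7. A simulation with two strata of 16, allocated 8/8, gave mean half-widths of 0.70/0.63/0.52 adjusted and 0.85/0.72/0.56 for change scores.

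**4. Units (secondary).** SD of change = single-time-point SD × √(2(1 − rho)). A true difference of 1 single-time-point SD is therefore 1/√1.4 = 0.85, 1/√1.0 = 1.00 or 1/√0.6 = 1.29 in SD-of-change units. The two scales agree only at rho 0.5.

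To see what a later mix-up could do, assume a true effect of 0.5 single-time-point SD and 80% power:

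- A pilot d in change units (0.42/0.50/0.65), read as single-time-point SD for a baseline-adjusted trial, plans 81/49/21 per arm where 59/49/34 are needed.
- A single-time-point d of 0.50, used for a change-score trial, plans 64 per arm where 89/64/39 are needed.

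For scale, a pilot d of 0.5 at 16 per arm has SE ≈ √(2/16 + 0.5²/64) = 0.36, so its 95% CI runs from about −0.20 to 1.20. The unit shift is 0.42 − 0.50 = −0.08 to 0.65 − 0.50 = +0.15.

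**The case against.** The strongest reply is that the contrast is already settled. Section 4.2.1 names it, Aim 1's summaries yield it by subtraction, and Aim 2a shows that individual change scores will be computed. The pooled-variance test in section 10.5, read with an endpoint defined as change, points to a change score scaled by the pooled SD of change. The study is a pilot that disclaims inference, and Aim 1 is written as description throughout. Section 8.8 keeps the de-identified data, so any contrast or SD can be recomputed later.

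Much of this stands. A reader might infer that the primary endpoint cannot be estimated, or that the plan has put a within-arm or post-only result in its place. The documents do not support that: section 4.2.1 rules out both as the primary effect, and the data for the right contrast are collected. A reader might also take the full standard error of the TP0 group difference (0.35 SD) as bias in the post-only contrast. Only rho × 0.35, or about 0.11/0.18/0.25 SD, carries through, and the 0.72 half-width already includes it.

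What does not stand is that the SD is fixed. Section 10.5 never names its outcome variable, so the change-SD reading is an inference. Subtraction gives a raw point estimate but does not decide between a change score and baseline adjustment. Recomputing later means making both choices with the results in view.

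**Conclusion.** The point holds as an omission worth correcting. For all three modalities Aim 1 lists summaries that are not the primary contrast, and no document states the SD behind the effect size. Compared with a change score, naming the adjusted contrast narrows the 95% CI half-width from 0.85/0.72/0.56 to 0.69/0.63/0.52 SD.

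These figures rest on an assumed rho of 0.3/0.5/0.7, equal SDs and independent participants. Both arms are delivered in groups over recruitment cycles (sections 5.5 and 6.1.1), and any clustering would alter the half-widths.

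A reader might conclude that the unnamed SD will mis-size the R01 trial. The documents do not support that as a prediction. It needs a later unit error on retained data, it vanishes at rho 0.5, and the shift is smaller than the pilot's own sampling error. Nor is there any fault in the stated power.

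**What to change.** Add to SAP Aim 1, for each modality:

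> The primary estimate is the MBSR-minus-HEP difference in the TP1 ROI parameter from a linear model with the TP0 value and chemotherapy stratum as covariates. It is reported raw and standardised by the pooled TP0 SD, with a 95% CI. The observed TP0-TP1 correlation is also reported.

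Keep the pre-intervention group differences and the within-arm changes as description. A change-score or group-by-time contrast with its SD named would also close the gap; the adjusted model is preferred for its narrower interval. Reporting the correlation lets a later planner convert between SD scales.

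The wording applies to each ROI parameter and does not choose among ROIs or modalities. The cost is SAP text and two degrees of freedom (30 to 28), because both covariates are already collected: TP0 is scanned, and chemotherapy stratifies the randomisation (section 10.6.1). Sample size and data collection do not change.
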